3.8. Baseline patient demographics and clinical data collection

After patient recruitment, baseline characteristics including age, sex, body weight and height, ASA grading, important past health comorbidities (hypertension, diabetes mellitus, significant cardiovascular diseases, known hemolytic conditions/hemoglobinopathy), medication history will be collected. The information regarding baseline hematological profile (hemoglobin level, ferritin level) at the time of recruitment will be recorded.

3.9. Standard perioperative care apart from the study interventions

Standard anaesthetic preoperative assessment will be carried out either in the preoperative assessment clinic or by the list anaesthetist on the day before surgery, according to the routine practice in our hospital for all elective colorectal cases. Patients are allowed to continue their usual medications as directed by the parent surgical team and case anaesthetists. Upon recruitment, patients will not receive iron supplements other than intravenous iron isomaltoside.

Following the existing practice, patients for elective colorectal cancer resection operations are admitted to surgical wards one day before the operation. The second batch of study blood tests (including complete blood count, iron profile) will be taken along with cross match on admission. Bowel preparation will be undertaken if deemed necessary by the parent team.

General anaesthesia will be provided by anaesthetists blinded to the study allocation, without restrictions on the anaesthetic agents and analgesic modalities to be used. As per usual practice within the department, intravenous induction will be achieved with propofol and fentanyl, followed by maintenance with sevoflurane/desflurane. Muscle relaxation with non-depolarizing muscle relaxant (atracurium/cisatracurium/rocuronium) will be maintained throughout the operation, followed by reversal with neostigmine/atropine at the end of operation. Analgesia will be achieved by multimodal approach, by a combination short and long acting opioids (fentanyl/morphine), tramadol, paracetamol, non-steroidal anti-inflammatory drugs (NSAIDs) and local anaesthetics (intravenous infusion and/or local infiltration) at the discretion of the list anaesthetists. Antiemetics will be given as routine either with ondansetron, dexamethasone or metoclopramide.

After the surgery, patients will be managed in surgical wards under the colorectal team. Fluid sips and diet will be resumed and stepped up as soon as tolerated usually starting on postoperative day one. Study blood sample (hemoglobin level, iron profile) will be taken with the other routine blood tests on postoperative day one. Patient will be discharged home as long as adequate recovery is achieved and discharge criteria are met as decided by the parent surgical team. Before patient discharge, patients will be approached by research personnel to fill in a questionnaire (QoR 15 Chinese version) assessing the quality of recovery outcome on third day after surgery.

Throughout the perioperative period, the decision to transfuse blood is based on clinical judgment by the parent surgical team and list anaesthetists, who are blinded to the patients' group allocation. There is no specific transfusion trigger defined in this study

protocol as it might vary among patients with different needs, for example, patient with history of ischemic heart disease or stroke may have a higher transfusion trigger.

3.10. Intervention: intravenous iron isomaltoside(Monofer®)

Patients randomized to the treatment group will be given a dose of intravenous iron isomaltose in the time frame of 3-10 weeks before operation date. The dose will be determined by the patient's body weight: > 50kg: 1000mg; <50kg: 20mg/kg body weight, to be infused over 30 minutes. The infusion would take place in the day surgical unit and patients will be closely monitored. Vital signs would be charted before, at 15 minutes during infusion and immediately after the infusion. Patients will be discharged home on the same day if no adverse reactions are observed.

2 weeks after intravenous iron isomaltoside administration, blood test for hemoglobin level and iron profile would be repeated. Subjects with hemoglobin level less than 10g/dL will receive a second dose of intravenous iron isomaltoside. The second dose would be identical to the first dose i.e. body weight: > 50kg: 1000mg; <50kg: 20mg/kg body weight, to be infused over 30 minutes. Similar as before, intravenous iron administration would take place during a day admission to the day surgical unit with monitoring.

3.11. Control: Standard care

Patient randomized to the control arm will follow the standard perioperative care as described above and the perioperative management they received will be identical to the treatment arm except no intravenous iron isomaltoside will be given.

3.12. Follow up/assessment

Data on the primary and secondary outcomes as listed above would be collected. Investigators will access the patients' records via the Hospital Authority computer system and the hardcopy documents in the wards. Data on the hematological profile throughout study period (on diagnosis, preoperative day, post-operation day one, on discharge) will be retrieved from the computer records. The number of red cell transfusion will be retrieved from the computer records as well as counterchecking with

anaesthetic records/progress notes. The length of hospital stay (for the operation and DAH₃₀) will be counted by referring to computer patient records.

The quality of recovery is assessed by a self-reported quality of recovery questionnaire (QoR-15)¹³, which assess different dimensions of recovery including pain, physical comfort, physical independence and mental well-being.

4. Statistical analysis

Missing data will be checked and imputed to preserve power. The Shapiro-Wilk test will be used to check data for normality. Generalized estimating equations will be used to examine the changes in haemoglobin level and serum ferritin levels over time. Expected skewed data, such as the quality of recovery score, the number of days of hospital stay, units of transfusion and DAH₃₀, will be reported as median and interquartile range, and compared between treatment arms by Mann-Whitney U tests. Two-tailed χ^2 test will be used to analyze categorical data between groups. All of the analysis would be intention-to-treat and with a statistical significance level defined at $P < 0.05$.

5. Expected impact on study/patient care

This pilot study is crucial for refining the design for a larger scale, prospective RCT in the future. The effect size in the primary outcome measures obtained in this study will help determine sample size for the larger study; based on sample size and the recruitment rate, the enrolment duration can be estimated. Although intravenous iron has been advocated as a more convenient and effective alternative to oral iron therapy in terms of raising ferritin level and preoperative haemoglobin level, it remains to be determined whether these increases in laboratory parameters translates into significant improvement in patient outcomes or quality of recovery. Intravenous iron does come with additional cost and admission. Whether this can be offset by a reduction in transfusion rate, and hospital length of stay will require a further cost-effectiveness analysis in future. The study may provide useful evidence in writing a clinical protocol for managing preoperative iron deficiency anaemia in colorectal cancer surgical patients with the ultimate aim of reducing exposure to allogenic blood products and improvement in patient outcomes.

6. Potential hazards, Safety and audit

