transfusion rate and hospital stay is thus expected, which implies that a large sample size would be required to conduct a RCT with adequate statistical power. Before embarking on such a large-scale research project, it is necessary to conduct a feasibility trial to estimate recruitment rate, sample size and allow proper logistics management.

There are two areas to be assessed in this pilot trial including study process and the predicted effect size.

2.1. Study process:

The number of patients diagnosed with colorectal cancer listed for elective resection per month will be studied, and the prevalence of iron deficiency anaemia among these patients will be recorded. All of the eligible patients satisfying the recruitment criteria stated below would be invited to join the pilot study, and the refusal rate will be noted. The information is required to calculate the recruitment rate of the study. The median waiting time for surgery will also be calculated. We envision that a recruitment rate of more than 60%, 5 patients per month and a median waiting time of 4 weeks will be necessary for conducting a larger RCT.

2.2. Effect size:

In this pilot trial, we plan to explore the effect size of the primary outcomes for the proposed RCT, including haemoglobin rise and serum ferritin rise associated with the intravenous iron treatment group compared to standard care. The secondary outcomes to be measured will include perioperative blood transfusion rate, hospital length of stay, quality of recovery scores, surgical complications, adverse reactions and days (alive and) at home within 30 days of surgery (DAH₃₀). As stated before, the baseline transfusion rate for elective colorectal surgeries in our population is lower compared to international studies, therefore it would be inaccurate to use existing data to estimate the sample size.

[figure not shown]
3. Study Design

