3.1. Methodology

A single-centered, superiority, 2-arm, randomized controlled trial is planned to

determine the efficacy and safety of preoperative intravenous iron isomaltoside (Monofer®) therapy compared to standard care (control) in colorectal cancer patients undergoing elective tumour resection surgery. The study design is outlined in the diagram in Figure 1.

Figure 1. Overview of study design

For the pilot study to assess the feasibility of conducting the actual large-scale trial, 40 patients (20 in the treatment arm and 20 in the control arm) will be recruited. The study design of the pilot study would be identical to the above-proposed trial with the aim to explore the study process and the predicted effect size.

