3.2. Study population

Consecutive patients diagnosed with colorectal cancer listed for elective curative tumour resection surgery (including open and laparoscopic approach) will be screened for eligibility based on the criteria listed below. Baseline blood tests (including: complete blood counts, renal and liver function, iron profile (serum ferritin, transferrin saturation/TSAT), serum B12 and folate) will be collected as a routine preoperative workup.

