3.6.1. Effect size

Primary Outcomes:

- Preoperative change in hemoglobin concentration (g/dL) and change in serum ferritin (mcg/L), which is, the difference between the value at diagnosis and preoperative day.

Secondary Outcomes:

- Units of red blood cells transfused in perioperative period in the two groups, defined as:
 1. Preoperative - from randomization to operation;
 2. Intraoperative – inside operating theatre and recovery room;
 3. Postoperative - from arrival to ward after operation to discharge.
- Duration of hospital stay (days).
- Quality of recovery as measured by questionnaire (QoR-15(Chinese)) completed on postoperative period. The QoR-15 (See Appendix A) includes the items measuring pain, physical comfort, physical independence, psychological support and emotional state.¹³ The QoR-15 score ranges from 0 to 150 and takes about 3 minutes to complete.¹³ The validity (convergent, construct, discriminant), reliability (internal consistency, split-half, test-retest), responsiveness,

acceptability and feasibility properties have been well established.¹³

- Incidence of adverse reactions/serious adverse events to intravenous iron administration and adverse reaction to blood transfusions (Adverse reactions: any unintended responses related to drug/blood products administrations e.g. skin rash, pain, neurological/respiratory/cardiovascular symptoms. Serious adverse events: life-threatening/require additional period of hospitalization/results in disability/mortality eg. Anaphylaxis, acute hemolytic transfusion reactions, organ failure etc.).
- Rate of surgical complications recorded and graded according to Clavien Classification of Surgical Complications.¹⁴ (See Appendix B)
- Days (alive and) at home within 30 days of surgery (DAH₃₀)
 - A parameter incorporating the duration of initial hospital stay associated with the index surgery, re-hospitalization due to post-discharge complications, discharge to institutional care and early deaths within 30 days post operatively. It has been validated as an effective patient-centered outcome measure for perioperative trials.¹⁵
 - Method of calculation – refer to Appendix C

3.6.2. Study process:

- Patient recruitment rate (number of recruited patient/total number of eligible patients x 100%)
- Number of patients recruited per month.
- Median waiting time to surgery (days).

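### Section 4 does not tie its GEE of haemoglobin and ferritin "over time" to the preoperative between-arm contrast that defines the primary outcomes; a baseline-adjusted preoperative comparison with a t-based interval should be named.

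*Combined protocol and SAP*

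**What the plan says.** Section 3.6.1 defines each primary outcome, the preoperative change in haemoglobin (g/dL) and in serum ferritin (mcg/L), as "the difference between the value at diagnosis and preoperative day". Section 2.2 gives the comparison: "haemoglobin rise and serum ferritin rise associated with the intravenous iron treatment group compared to standard care". So the endpoint, the interval and the comparator are stated.

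Section 4 gives the analysis in one sentence: "Generalized estimating equations will be used to examine the changes in haemoglobin level and serum ferritin levels over time". Section 3.12 lists the haematology times as "on diagnosis, preoperative day, post-operation day one, on discharge". Section 4 applies intention-to-treat throughout, "with a statistical significance level defined at" P < 0.05, and plans to impute missing data. For the skewed outcomes and the categorical outcomes it does state a comparison between arms or groups.

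On size and purpose, section 3.1 says "40 patients (20 in the treatment arm and 20 in the control arm) will be recruited", and section 5 says "The effect size in the primary outcome measures obtained in this study will help determine sample size for the larger study".

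**The concern.** The sentence on the primary outcomes contains no arm term, target visit, baseline adjustment, type of standard error, reference distribution or confidence interval. An analyst could follow it faithfully and fit any of three things:

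- an arm-by-visit model, reading off the preoperative contrast;
- an arm effect averaged over the post-baseline visits;
- a joint test of arm by time.

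Only the first answers the question in section 3.6.1. The other two bring in values from postoperative day 1 and discharge, which also reflect surgical blood loss and transfusion.

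At stake is the effect size passed to the larger trial, and the interval around it. With 20 patients per arm, the choice of standard error and reference distribution also has a visible effect on that interval.

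**Working it through.** The plan gives no power, SD or effect size for its 40 patients, so there is no figure of its own to reproduce. The checks below are illustrations with stated inputs.

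**1. Which effect is estimated.** Set the preoperative arm effect to 1 and assume that it is half that on postoperative day 1 and at discharge. An arm effect averaged over the three post-baseline visits is (1 + 0.5 + 0.5)/3 = 0.67 of the target. The documents do not give the postoperative effect. If it equalled the preoperative effect, the average would be 1.00.

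**2. Standard error and reference distribution.** Inputs: 20 per arm (section 3.1) and the haemoglobin IQRs of the cited randomised trial in section 1. That trial's comparator was oral iron, and normality is assumed.
- SDs: (2.58 - 0.93)/1.349 = 1.223 and (1.33 + 0.13)/1.349 = 1.082, pooled 1.155 g/dL.
- SE of the difference in change: 1.155 × √(2/20) = 0.365.
- 95% half-width with t on 38 df: 2.024 × 0.365 = 0.74 g/dL.
- With an uncorrected sandwich SE and z: 1.96 × 0.365 × √(19/20) = 0.70 g/dL.
- Type I error of that second version: 2P(t38 > 1.96 × √(19/20)) = 6.4%, so coverage is 93.6%. Fitted GEEs (2,000 replicates) gave 6.5%.
- A joint 3-df arm-by-time Wald test with uncorrected SEs gave 9.0% (20,000 replicates, normal data, exchangeable correlation 0.6 assumed).
- Under the same assumptions, a GEE with bias-reduced SE and t38 gave 4.4% (2,000 replicates), and ANCOVA with a t reference gave 5.1% (20,000 replicates).

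**3. Baseline adjustment for haemoglobin.** With complete data, the preoperative contrast from a saturated arm-by-visit GEE equals the unadjusted difference in change scores. With ρ the correlation of baseline with preoperative value, and k the baseline SD divided by the preoperative SD (both assumed), the variance of ANCOVA relative to the change score is (1 - ρ²)/(1 + k² - 2ρk) × 37/36.

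| ρ | k = 1 | k = 0.7 |
|---|---|---|
| 0.3 | -33% | -13% |
| 0.5 | -23% | -2% |
| 0.7 | -13% | +3% |
| 0.9 | -2% | -15% |

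The ratio is largest at ρ = k, where it is 37/36 = 1.028. With equal arm variances the cost therefore cannot exceed 2.8%. The ANCOVA half-widths over this grid run from 0.60 to 0.75 g/dL, against 0.74 unadjusted.

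**4. Ferritin.** The documents give no SD or correlation. They do cap baseline ferritin at 100 mcg/L (section 3.3), and one arm then receives intravenous iron, so skew and unequal spread are likely. A simulation assumed a baseline median of 20 mcg/L truncated at 100, a treated preoperative median of 300, and log-SDs of 0.5, 0.7 and 0.9. The raw-scale ANCOVA t-interval missed the true difference about 8% to 13% of the time, rising with the log-SD. The same model on log ferritin missed about 5% of the time.

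**The case against.** **The target can be inferred.** Sections 3.6.1 and 2.2 fix the endpoint, interval and comparator, and a saturated arm-by-visit GEE recovers the contrast. This stands. GEE is not an error, and a reader should not infer that the primary comparison is undefined throughout the protocol. What is missing is the link in section 4.

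**The plan names no faulty standard error.** This also stands. A reader might infer that the trial will run at 6.4% type I error, but the documents do not support that: they name neither the sandwich SE nor the z reference, and a corrected GEE holds its size. The figure describes one possible default.

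**The pilot is about feasibility.** The only numeric conditions for a larger trial are process ones (section 2.1: recruitment above 60%, 5 patients per month, a 4-week median wait), and section 5 says only that the effect size will help. This limits the weight of the point. It does not remove it, because estimating effect size is one of the pilot's two stated purposes.

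**The precision gain is uncertain.** A reader might infer that ANCOVA is clearly more precise. Entry requires haemoglobin below 13 g/dL, which probably compresses the baseline SD and points to k below 1. At k = 0.7 and ρ of 0.5 to 0.7 the change is only -2% to +3%. Some cells are implausible: k = 1 with ρ = 0.9 implies a baseline SD of 1.155/√0.2 = 2.58 g/dL. The objection stands, and no gain should be promised.

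**Raw-scale ANCOVA may serve ferritin badly.** The simulation supports this, so the fix treats ferritin separately.

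**Conclusion.** The point holds as a gap between the endpoint and its analysis, and it should be closed before the data are analysed. Its main consequence is that a visit-averaged or joint-test result could stand in for the preoperative contrast. The 0.67 dilution illustrates this and depends wholly on the assumed postoperative effect.

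The inferential consequence is smaller and conditional: about 1.4 percentage points of excess type I error for a single contrast, if uncorrected SEs and z are used. The case for baseline adjustment is that it targets the stated endpoint and, for haemoglobin, costs at most about 3% in variance while possibly saving up to about a third. These figures rest on SDs from a trial with a different comparator and on assumed ρ and k. No precision gain is claimed for ferritin.

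**What to change.** Add to section 4: for each marker, the primary analysis is the between-arm difference at the preoperative day, adjusted for that marker's pre-randomisation baseline value, by ANCOVA with a t-based 95% CI. A baseline-constrained GEE with bias-corrected standard errors and a t reference is an equivalent choice. State that this estimate is the one carried into sizing the larger trial, and that postoperative day 1 and discharge values are secondary. For haemoglobin the result stays in g/dL; with baseline in the model, analysing the change or the preoperative value gives the same arm difference.

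For ferritin, fit the baseline-adjusted model to log ferritin for inference, report the ratio of geometric means, and give the raw change in mcg/L descriptively.

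No new samples are needed. Section 3.2 already provides "Baseline blood tests (including: complete blood counts, renal and liver function, iron profile (serum ferritin, transferrin saturation/TSAT), serum B12 and folate", and section 3.9 already takes a blood count and iron profile on admission the day before surgery. The costs are one parameter spent on baseline, a ferritin effect expressed as a ratio instead of a difference, and, under ANCOVA, reliance on the imputation already planned for any patient without a preoperative sample.

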Submission Date/version: 3rd March, 2018/Version 1

Study Title: Efficacy of preoperative intravenous iron isomaltoside in colorectal cancer surgical patients with iron deficiency anaemia compared to standard care: a pilot randomized controlled trial

Principal Investigator: [name] [name] (1)

Co-investigators: [name] [name] (2), [name] [name] (1), [name] [name] (3), [name] [name] (3)

(1) Department of Anaesthesia and Intensive Care, Prince of Wales Hospital, Hong Kong

(2) Department of Anaesthesia and Intensive Care, The Chinese University of Hong Kong

(3) Division of colorectal surgery, Department of Surgery, The Chinese University of Hong Kong

Area of Research: Perioperative medicine - patient blood management

Abstract: Iron deficiency anaemia is a common condition among colorectal surgical patient. Untreated anaemia would lead to increase in blood transfusion, surgical complications and mortality. Treatment with oral iron sulphate is poorly tolerated due to side effects. Intravenous iron supplement provides an alternative way to rapidly replace iron deficit during the preoperative period among surgical patients. Evidence is growing for its effect in rising hemoglobin level and reducing blood transfusion, at the same time supporting its safety profile.

We plan for a single-centered, randomized controlled trial to examine the effect of intravenous iron compared to standard care in terms of hemoglobin level/serum ferritin increment, need for blood transfusion, duration of hospital stay, quality of recovery and surgical complication rate, as well as safety profile among colorectal cancer surgical patients in Hong Kong. We propose the following pilot RCT for exploring the effect size and study process in conducting the above-mentioned large-scale RCT.

1. Background

Iron deficiency is the most common nutritional deficiency in the world, with approximately two billion people worldwide suffering from the condition according to World Health Organization data in 2001.¹

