3.7. Randomization, allocation concealment and blinding

Recruited patients would be prospectively randomized to either preoperative intravenous iron isomaltoside (treatment group) or standard care (control group). The 1:1 allocation will be performed by one of the investigators, not involved in patient care or study assessment, using a computer program PASS 14.0 (NCSS, Kaysville, UT). The treatment allocation will be concealed in sealed opaque envelopes and handed over to third party anaesthetists (other than the investigators) for arranging pre-operative

intravenous iron therapy for patients in the treatment arm, or no therapy in the control arm.

Records related to the iron administration will be kept away from the investigators and the parent surgical team for the duration of the study period to reduce performance bias. Patients in both arms will not be blinded to the treatment they may receive in the management of perioperative anaemia, be it intravenous iron in the treatment group, or any necessary perioperative blood transfusions in either groups. An alert in the patient's electronic records will be implemented to remind the parent surgical team and the case anaesthetist that the patient is participating the study, however the both parties will be blinded to the patients' group assignment, to avoid interference to their transfusion decision.

Unblinding will be done only in the condition where clinician believes that clinical management depends importantly on whether the patient received intravenous ferric isomaltoside. Unblinding will be achieved by contacting the investigators, and any unblinding event and the reason of unblinding will be recorded.

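### Section 4 plans no between-arm estimate or confidence interval for quality of recovery, hospital stay, DAH30 or complications, although section 3.6.1 lists them under Effect size

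*Combined protocol and SAP*

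**What the plan says.** The abstract describes a "pilot RCT for exploring the effect size and study process", and section 3.1 sets its size: "40 patients (20 in the treatment arm and 20 in the control arm) will be recruited". Section 3.6.1, headed Effect size, lists both the primary outcomes (change in haemoglobin and in ferritin) and the secondary outcomes, among them hospital stay, QoR-15, Clavien-graded complications and DAH30.

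Section 4 is the whole analysis plan. Outcomes expected to be skewed, including QoR-15, stay and DAH30, "will be reported as median and interquartile range, and compared between treatment arms by Mann-Whitney U tests". For complications the only applicable sentence is "Two-tailed χ^2 test will be used to analyze categorical data between groups". The closing rule is "All of the analysis would be intention-to-treat and with a statistical significance level defined at" P < 0.05. No section names a between-arm difference, a ratio or a confidence interval for any of these four outcomes. The confidence intervals in the Background belong to a cited systematic review.

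Two sentences limit the point. Section 2.2 ties the exploration of effect size to the primary outcomes and says that the secondary outcomes will be measured. Section 5 says that the primary-outcome effect size will inform the size of the later trial.

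**The concern.** A median and IQR for each arm plus a P value is neither an effect size nor a statement of its precision. Yet section 3.6.1 files these outcomes under that heading. Section 2 gives an expected smaller effect on transfusion and stay as a reason for needing a pilot, and section 5 leaves open whether laboratory gains become better outcomes or recovery.

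Two features of the setting add to this. Stay and DAH30 are counted in whole days in a short-stay pathway, so arm medians can coincide when the distributions differ. And with 20 per arm the tests have little power for modest effects, while the only criterion in the plan is P < 0.05. Nothing labels the secondary tests exploratory, and section 3.1 calls the design a superiority trial. A report that follows section 4 literally could contain a row of non-significant results and nothing to show how large a benefit or harm remains compatible with the data.

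**Working it through.** **Inputs from the documents.** 20 per arm (section 3.1), 1:1 allocation (section 3.7), significance level 0.05 (section 4). Two-tailed testing is stated for the chi-squared test only; I assume it for Mann-Whitney. The plan gives no power, SD, event rate or target difference for these outcomes, and N = 40 has no derivation, so there is no stated figure to reproduce. All effect sizes below are assumptions.

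**1. Mann-Whitney power.** Approximated by a two-sample t test with effective n = 20 × 0.955 = 19.1 per arm (the efficiency under normality). The noncentrality is d × √(19.1/2) = 3.09d, on 36.2 degrees of freedom.

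| Standardised difference d | Noncentrality | Power |
|---|---|---|
| 0.2 | 0.62 | 9% |
| 0.3 | 0.93 | 15% |
| 0.5 | 1.55 | 32% |

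Power reaches 80% at d = 0.93. The normal approximation gives almost the same answers: 9%, 15% and 34%, and 80% at (1.960 + 0.842) × √(2/19.1) = 0.91.

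**2. Complications.** Power for two proportions at 20 per arm is 9% for 10% v 5%, 14% for 20% v 10%, 20% for 30% v 15% and 28% for 40% v 20%.

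**3. What the missing intervals would show (95% half-widths).**
- Mean difference: 2.024 × √(2/20) = 0.64 SD.
- Mann-Whitney probability near the null: 1.96 × √(41/(12 × 20 × 20)) = 0.18.
- Risk difference (Wald): for 10% v 5%, 1.96 × √(0.09/20 + 0.0475/20) = 16 points; for 40% v 20%, 1.96 × √(0.24/20 + 0.16/20) = 28 points.

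**4. A single table of complications.** Take 4/20 v 0/20 as an illustration. The Wilson limits are 8.1% to 41.6% and 0% to 16.1%. The Newcombe interval for the 20-point difference is therefore
- lower: 20 − √((20 − 8.1)² + (16.1 − 0)²) = −0.1 points (with unrounded limits);
- upper: 20 + √((41.6 − 20)² + 0²) = +41.6 points.

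Uncorrected chi-squared gives P = 0.035, the continuity-corrected version 0.114 and Fisher 0.106. Which test variant to use is a separate question. The relevance here is that the interval conveys the uncertainty whichever variant is chosen.

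**5. Whole-day stay.** Simulation of 6,000 trials, assuming rounded lognormal stays, control median 5 days, log-SD 0.45 and a true 10% shortening (about half a day). Arm medians are identical in about 23% of trials and P < 0.05 occurs in about 10%. The Hodges-Lehmann difference, a natural companion to Mann-Whitney, is exactly 0 in about 43% of the same trials. As a point estimate for whole-day data it hides a real shift more often than subtracting medians does.

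**The case against.** The strongest reply is that the plan never promised effect sizes for these outcomes. Sections 2.2 and 5 attach that purpose, and the sizing of the next trial, to haemoglobin and ferritin. The sentence "therefore it would be inaccurate to use existing data to estimate the sample size" follows from the local transfusion rate and not from any outcome discussed here. The rationale in section 2 covers stay, but not QoR-15, DAH30 or complications. This stands: the case rests on the heading of 3.6.1, the general line in the abstract and the rationale for stay.

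It can also be said that naming a test does not forbid an interval, that medians and IQRs allow a crude difference and a rough SD, and that section 7 retains the raw data for at least 3 years. That is fair, so it would be wrong to say that the later trial is left with nothing usable. But a crude difference has no interval, and whether one is reported is left to chance.

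A reader might infer that null results will be reported as no effect. No section says so, and section 5 is cautious about patient outcomes; the most that can be said is that no safeguard is written. A reader might also infer that the tests must fail whatever the truth. They need not: power is 80% near 0.93 SD. And section 2 expects an effect smaller than in published work (where stay was 8.4 v 10.9 days), which is not the same as a small one.

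**Conclusion.** The point holds as a gap in planned reporting for four secondary outcomes. It biases no result, does not change the sample size, and leaves the stated primary aim untouched. Section 4 supplies only arm summaries and tests for QoR-15, stay and DAH30, and only a test for complications.

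At 20 per arm, non-significant results are likely unless effects are large. A non-significant result would typically remain compatible with differences of around 0.6 SD, or 16 to 28 percentage points for complications. These sizes depend on the assumed standardised differences and complication rates, and the tied-median figures on the assumed stay distribution, because the documents give no local values. That the plan contains no between-arm estimate or interval for these outcomes depends on none of those assumptions.

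**What to change.** Amend section 4 as follows.

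- **Stay, DAH30 and QoR-15:** keep the median and IQR by arm. Add the mean and SD by arm, the between-arm mean difference with a bootstrap 95% CI, and the Mann-Whitney probability with 95% CI. A Hodges-Lehmann interval may be added, but should not lead for the whole-day outcomes.
- **Complications:** report counts by Clavien grade and arm. Add the risk difference with a Newcombe 95% CI for one dichotomy fixed in advance, for example any complication.
- **Interpretation:** label P values for secondary outcomes exploratory, and state that no claim of efficacy or of no effect will rest on P < 0.05.

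The cost is a few sentences in the analysis section; patients, data and procedures are unchanged. The downside is that secondary outcomes can no longer be labelled significant.
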